### Initial Pilot Intervention Study

Following development of all intervention materials, in the spring of the first year we will conduct a multiple baseline design across at least three classrooms to investigate the preliminary effectiveness of our approach to promoting positive student outcomes. In the spring of the first year, once initial intervention materials are developed, we will begin collection of concurrent baseline data for a child with ADHD and young for the grade from at least three participating classrooms. Then, one classroom will be assigned to begin intervention based on an analysis of baseline stability, level, variability, and trend and subsequent classrooms will be introduced to intervention using the same criteria at later timepoints. Thus, the project will be a concurrent multiple baseline design across classrooms, with intervention implemented in systematic steps across classrooms at varied timepoints. This will allow for an evaluation of the initial scientific premise of the developed intervention, and provide a context for the investigators to assess implementation of treatment, timely collection of measures, feasibility of procedures, and collect information on teacher satisfaction and suggestions for modification. The scientific rigor of this pilot study will be supported through an adherence to What Works Clearinghouse Standards for single-case design research (What Works Clearinghouse, 2019).

Specifically, teachers will be asked to complete a direct behavior rating (DBR) each day during a specified time period where the child exhibits challenging behavior. DBRs are brief ratings of student behavior (Briesch et al., 2016; Chafouleas, Riley-Tillman, & Sugai, 2007; Fabiano et al., 2017). DBRs will serve as the ongoing, progress monitoring measure in this pilot study. For example, following group instruction in reading, the teacher might circle a number on a scale from 0-10 to indicate the degree to which the student was actively engaged. The study will use the most studied target behaviors - Academic Engagement (AE), Disruptive Behavior (DB), and Respectful Behavior (RS) at the end of each targeted intervention session for each student. Inter-rater agreement will be collected on the DBRs by having an observer in the classroom for at least 20% of days for the same time period and completing identical DBR-SIS ratings as well as the SBTR observation. Teachers will complete all measures at initial baseline data collection, and at the end of the treatment. Child-based neurocognitive measures will be completed at the initial baseline data collection period and at the end of treatment. Thus, we will gain information on the feasibility of data collection to inform our larger, between group pilot study during this initial pilot as well.

### Pilot Study of RAE Prevention Timing and Effectiveness

To explore the relationship between the hypothesized mechanisms of treatment and key outcomes, a small randomized trial will be conducted to investigate the feasibility and promise of the proposed treatment for modifying the hypothesized treatment targets. It is currently unclear when the RAE prevention should be optimally implemented. On

the one hand, it may be beneficial to work with teachers immediately upon school entry, prior to the development of frequent relative comparisons that disadvantage the relatively young child in the class with ADHD. On the other hand, one might speculate that the intervention may be better positioned to promote teacher change after they have had frequent experiences with the child, and the relative comparisons have occurred, providing an active target for modification through intervention. Teacher acceptance and intervention feasibility may also vary based on implementation timing. Therefore, a pilot trial will be conducted that can compare the feasibility, effectiveness, and acceptability of these two competing intervention initiation timepoints, compared to a no intervention condition.

The sample of kindergarteners will be drawn from the school districts in Erie County. During the summer preceding each academic year, the UB researchers will partner with the school districts to attend kindergarten screening visits. All children who will enroll in kindergarten for the upcoming fall must come to the district office or designated school to enroll in the kindergarten year. We will partner with district administrators to provide time for study staff to introduce the study and request parental consent for participation. We will include all children born between 8/1 and 11/30 of the current school year. Specifically, children born in the

months of August, September, October, or November will be designated as relatively young for kindergarten.

The informed consent process will include a discussion of the risks/benefits of the planned study approach, and inform parents of their alternative choice (enroll in kindergarten as usual). Our enrollment plan is feasible given the overall level of kindergarten enrollment each year. We expect to enroll 30 participants per year.

Inclusion criteria will include a child who is: (1) enrolling in kindergarten for the first time; (2) has a date of birth is between 8/1 and 11/30 of the current academic year; (3) does not have an Individualized Education program for behavioral concerns; and (4) has elevated symptom ratings of ADHD. Excluded will be any child outside of the targeted birthdate range, currently in restrictive special education placements for behavior (as this is a targeted study outcome), or taking psychoactive medication for mood, behavior, or inattention.

During kindergarten screening we will include children who have at least six symptoms endorsed at clinically significant levels via parent and/or preschool teacher ratings on the DBD rating scale across inattentive and/or hyperactive/impulsive presentations (Pelham, Gnagy, Greenslade, & Milich, 1992). Because we are exploring whether symptom ratings worsen during the school year, based on group assignment, we do not require a research-based, DSM diagnosis of ADHD, but expect our sample to illustrate symptom levels that place the child at risk for kindergarten classroom impairment due to ADHD. This approach also includes students who will eventually meet criteria for combined presentation, but exhibit primarily hyperactive/impulsive symptoms due to the lack of attentional demands in preschool/child care settings (Lahey, et al., 2005). Random assignment will be stratified by sex to distribute proportionally across groups. The project will purposely only include children born in the last quarter of the school year, as this is the key demographic of interest in the present proposal.

Children whose parents provide permission will be enrolled in (1) kindergarten as usual; (2) the RAE prevention intervention implemented immediately (i.e., in October following the assessment); or (3) the RAE prevention intervention implemented at mid-year (i.e., in February). Given variability in birthdays, the large number of kindergarten classrooms currently in the are targeted, and the modest study demands for parents, we expect to meet all recruitment targets outlined in this application. Children assigned to the RAE prevention groups will have a school psychologist consultant assigned to the student for the duration of the school year. The consultant will work with the child's primary teacher to provide the preliminary training on the RAE and positive classroom management strategies, and to establish a DRC over the course of two consultation visits.

For the positive behavioral support, target behaviors will be identified, operationally defined, and integrated into a DRC. The teacher will be asked to implement the intervention during the week between the first and second visit. At the second consultant visit, target behaviors will be refined, and using the data collected by the teacher, criteria for each target behavior will be modified (e.g., a child who averaged 10 verbally intrusive behaviors per class would have a target behavior changed to "Has 8 or fewer verbally intrusive behaviors"). DRCs will be implemented across settings and classes; however, a single teacher will be identified for assessment completion, observations will be conducted in that teacher's class. Parents will be invited to the school meetings, and the school psychologist will work with the parent to establish a menu of home-based privileges (e.g., screen time, bed time, extra parent-child activity time) that will be rewarded based on DRC performance each day. At the end of each day, the teacher will send the DRC home with the child so that the parent is provided feedback on a daily basis regarding the child's behavior at school. In addition to the home-based contingency management based on school feedback, which makes the child accountable at home for school-based behavior, the DRC serves as a mechanism of daily communication between the parent and teacher. Given the variability in behavior expected with a child with ADHD, such daily communication is often crucial for preventing deterioration in functioning and presents the parent and teacher with multiple opportunities to problem-solve.

After the initial meetings with the child's teacher, consultants will meet monthly with the teacher (and parent if available) via phone or video conference to provide feedback on the child's behavior during the month using a graphical representation of the child's DRC performance. This information will be used for data-driven decision making, a procedure shown to be better than teacher impressions/ judgments when intervention planning/monitoring (Fuchs et al., 2000). DRC goals will be adjusted as needed. It is expected that these monthly meetings will serve the purpose of ensuring goals are consistently addressed on the DRC throughout the year and that the goals set are developmentally appropriate for the child.

*Kindergarten as Usual (KAU) group.* Consultants will conduct an initial meeting with each teacher of children in the KAU group to describe study procedures and establish regular classroom observation times. This condition is conceptualized as a kindergarten as usual control and serves as the counter-factual condition.

Consultants will be M.A. level school psychology specialists or special education teachers appointed to the project. We have chosen to use individuals with these credentials to increase the external validity of the

intervention as these individuals are likely to be called upon to consult with teachers regarding the behavior of children with ADHD as well as be involved in the assessment of children with ADHD in many school districts.

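### Assignment appears to be by child although part of the treatment trains the child's teacher, and no rule covers a teacher shared between arms

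*Combined protocol and SAP*

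**What the plan says.** All references are to the combined protocol and SAP.

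- **Unit and stratification.** Under Pilot Study of RAE Prevention Timing and Effectiveness, children with parental permission go into one of three groups, and "Random assignment will be stratified by sex to distribute proportionally across groups". The consultant is attached to the individual student. The unit of randomisation is never stated; the child is the natural reading.
- **Treatment content.** In the two RAE arms the consultant works with the child's primary teacher "to provide the preliminary training on the RAE and positive classroom management strategies", and also sets up a daily report card (DRC) for that child. The argument for a February start is that "the intervention may be better positioned to promote teacher change after they have had frequent experiences with the child".
- **Who supplies the data.** For each child "a single teacher will be identified for assessment completion", and observations take place in that teacher's class. Under Assessment of Hypothesized Mechanisms of Treatment Effect, the teacher's ratio of positive to negative statements is read as a feature of the classroom and is collected in all three groups.
- **Control arm.** KAU "serves as the counter-factual condition". The consultant meets the KAU child's teacher to describe procedures and arrange observations. A teacher who also has a child in an RAE arm is not mentioned.
- **Size and timing.** "We expect to enroll 30 participants per year". Consent is sought "During the summer preceding each academic year". Assessments fall in October, January, May and the following October. Immediate treatment starts in October after the assessment, delayed treatment in February.
- **Analysis.** The Data Analysis Plan names group and time only.

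**The concern.** Training in general classroom management stays with the teacher and reaches every child in the room. If a KAU child shares a teacher with a child in an RAE arm, that teacher's ratings and positive-to-negative ratio enter the analysis as control values although the teacher has been trained. The same applies in January to a Delay child whose teacher was trained in October for an Immediate child.

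Aim two compares immediate and delayed RAE prevention with KAU, so the control values need to come from untrained teachers. The mechanism ratio is the most exposed measure, because it is the teacher's own behaviour. How exposed is unclear, since the text does not say whether statements are counted class-wide or only when directed at the observed child. Any such bias would not shrink as further cohorts are added, whereas the sampling error would.

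**Working it through.** There is no figure in the plan to reproduce: it gives no classroom count, power calculation, effect size, intraclass correlation (ICC) or allocation ratio. What follows is an illustration on stated assumptions.

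**Inputs.** From the documents: 30 children per year, three arms, training in October or February, assessments in January and May. Assumed: 10 children per arm; C classrooms with one teacher each, every child equally likely to be in any of them; carry-over f, the fraction of the treatment effect that reaches a control child of a trained teacher, of 0.25 to 0.75; a true standardised difference of 0.5; ICC 0.1 to 0.3.

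**Step 1: share of control children with a trained teacher.** In January only the teachers of the 10 Immediate children have been trained; by May the teachers of all 20 RAE children have.

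- January (KAU or Delay child): 1 − (1 − 1/C)^10
- May (KAU child): 1 − (1 − 1/C)^20

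| C | January | May | KAU children of 10, May |
|---|---|---|---|
| 50 | 18.3% | 33.2% | 3.3 |
| 100 | 9.6% | 18.2% | 1.8 |
| 200 | 4.9% | 9.5% | 1.0 |

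**Step 2: change in the contrast if carry-over is positive.** Proportion lost = f × share.

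- May: 4.6% to 13.7% at C = 100; 2.4% to 7.2% at C = 200; 8.3% to 24.9% at C = 50.
- January: 2.4% to 7.2% at C = 100; 1.2% to 3.7% at C = 200.
- With complete carry-over (f = 1, an upper bound, conceivable only for the teacher ratio) the losses equal the shares in the table.

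If f is negative, the contrast widens by the same arithmetic.

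**Step 3: comparison with sampling error.** The standard error of a difference between two arms of 10 is √(2/10) = 0.447 SD. For a true difference of 0.5, the largest May loss at C = 100 is 0.5 × 0.137 = 0.068 SD, or 0.068/0.447 = 0.15 of a standard error. The smallest at C = 200 is 0.5 × 0.024 = 0.012 SD. At C = 50 the largest is 0.5 × 0.249 = 0.125 SD, or 0.28 of a standard error.

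**Step 4: precision cost of assigning by teacher.** With weights w = ±1/(arm size), the variance of a contrast is (1 − ICC)·Σw² + ICC·Σ(sum of w within teacher)². Averaged over simulated placements, the ratio of standard errors, teacher over child assignment, is:

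| C | ICC 0.1 | ICC 0.3 |
|---|---|---|
| 50 | 1.04 | 1.09 |
| 100 | 1.019 | 1.045 |
| 200 | 1.010 | 1.023 |

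**Step 5: break-even.** Teacher assignment gives the better contrast-to-error ratio once f exceeds (1 − 1/ratio)/share. For C = 100 to 200 that is 0.10 (ICC 0.1) to 0.24 (ICC 0.3) in May, and 0.20 to 0.46 in January.

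**The case against.** Five arguments count against pressing this.

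- **Many classrooms.** The plan refers to "the large number of kindergarten classrooms currently in the are targeted". That makes sharing less common, but it is a remark about recruitment and no safeguard. On the assumptions above, the chance that at least one of 10 KAU children shares a trained teacher is still about 63% at 200 classrooms and 86% at 100.
- **Feasibility pilot.** Statistical Power gives priority to reliable implementation and disclaims effect-size estimation for an efficacy study. This stands and limits the weight of the point. The Data Analysis Plan nevertheless specifies group comparisons, and settling the randomisation procedure is itself a pilot's business.
- **Child-specific components.** The DRC, home rewards and monthly review belong to one child, so carry-over to child outcomes is probably partial. This stands.
- **Child-level assignment may be more precise.** If carry-over is below the break-even values, it is, slightly. This also stands, most clearly for the January contrasts.
- **Text not seen.** One passage was removed before review, and the Data Analysis Plan points to a description of deliverables that is not in the available text. A rule could be there.

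A reader might infer that the bias must run toward zero. The documents do not support that. The plan's own theory is that teachers compare children within a class, and only the classroom observers are described as blind. A teacher with one child on a DRC might rate or treat the KAU child worse by comparison, which would widen the contrast.

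**Conclusion.** The gap is real and worth closing, but modest. As far as the available text shows, following the plan as written allows one teacher to be both treated and counter-factual within a year. At an assumed 100 to 200 classrooms this touches about 1 to 2 of 10 KAU children by May. For a true difference of 0.5 and positive, partial carry-over, it moves the contrast by 0.01 to 0.07 SD against a standard error of about 0.45. Recruitment concentrated in fewer classrooms would make it larger.

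A reader might go further and conclude that the KAU comparison is contaminated or invalid. The documents do not show this: classroom count, carry-over, its sign, ICC, effect size and equal arms are all assumptions, and child-level assignment is itself inferred. What the text does support is that the unit of randomisation and the handling of shared teachers are left open, and that this can be settled cheaply before treatment starts but not undone after a teacher has been trained.

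**What to change.** 1. State the unit of randomisation.
2. Draw the allocation once each child's primary teacher is known and before treatment starts in October. Summer consent alone does not show that there is time, but the October assessment precedes immediate treatment and includes teacher ratings, so the teacher must be known by then.
3. Give all eligible children of the same teacher in the same year one arm.
4. Record and report any teacher trained earlier, in the Year 1 multiple-baseline pilot or for a previous cohort, and run a sensitivity analysis omitting those teachers' children. Neither exclusion of such teachers nor a limit of one child per teacher is needed.

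A teacher random intercept should not be required. Under random placement only about 2 (C = 200) to 4 (C = 100) teachers would have more than one enrolled child, too few to estimate that variance usefully.

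**Cost.** Sex balance and arm sizes become slightly looser. The standard error rises about 1% to 4% at 100 to 200 classrooms and about 4% to 9% at 50, for an ICC of 0.1 to 0.3. A child consented after the draw into an allocated class would have a known arm, so consent should close before the draw and a few late consenters could be lost. With the same classrooms and no teacher turnover, the sensitivity analysis for a second cohort would omit 30 × the May share: 2.9 children at C = 200, 5.5 at C = 100 and about 10 at C = 50. Three pilot classrooms would account for 30 × 3/C, or 0.45 to 0.9 of a child at 200 to 100 classrooms.

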### ***Outcome Measures.***

Outcome measures will be collected at the beginning of the kindergarten year in October, the middle of the kindergarten year in January, at the end of the kindergarten year in May, and at the beginning of the 1st grade year in October. These four assessment points will provide data on the proximal outcomes of the study manipulation and distal outcomes of the manipulation, and they will double as an assessment of the feasibility of the team's measurement plan and ability to retain participants in a longitudinal design (for both treatment and control groups).

#### ***ADHD-related Outcomes***

*Observations of Classroom behavior.* Independent observations will be conducted using the Student-Behavior Teacher-Response observation system (SBTR; Pelham, Greiner, & Gnagy, 2008; Vujnovic, Fabiano et al., 2014). The SBTR is an observation code that collects information on: (1) the frequency of student rule violations; (2) whether a teacher observed the misbehavior; (3) if observed, the teacher consequence employed and whether it was an appropriate consequence. The SBTR system also records the number of praise statements and commands issued. The SBTR is a well-defined and validated observation system for use with children with ADHD in classroom settings (Pelham, Fabiano, & Massetti, 2005). The SBTR has been successfully employed as a primary outcome in similar projects (Fabiano, Vujnovic et al., 2010; Fabiano et al., 2013; Pelham, Fabiano et al., 2016). Each observation will last for thirty minutes. Time of day and activity will be controlled. Observers will be blind to the child's treatment condition. To ensure the inter-rater reliability of this measure, 20% of observations will be completed simultaneously with a second observer.

*Disruptive Behavior Disorders (DBD) Rating Scale.* ADHD Diagnostic and Statistical Manual of Mental Disorders (DSM-IV; APA, 2000) symptoms will be measured using the DBD rating scale (Pelham et al., 1992), which will be administered to the child's teacher and parent. The DBD is a 45-item measure that asks parents to rate the DSM symptoms of ADHD, ODD, and CD on a 0-3 point frequency rating scale (i.e., *Not at all, Just a little, Pretty Much, or Very Much*). The 0-3 ratings will be summed across 18 ADHD symptoms and then an average score for ratings across symptoms will be computed for each individual.

*Impairment Rating Scale (IRS).* The IRS (Evans, Allen, Moore, & Strauss, 2005; Fabiano et al., 2006) is a rating scale that asks teachers to rate the severity of the child's problems and need for treatment and/or special services in important functional domains (i.e., relationship with peers, relationship with the teacher(s), academic progress, classroom functioning, self-esteem, overall need). There are six items on the scale, and scores on the measure range from 0 (Not a problem/Definitely does not need treatment or special services) to 6 (Extreme problem/Definitely needs treatment or special services). The average score for each of the individual domains rated were used in the analysis; scores could range from 0.0-6.0.

#### ***Academic Functioning***

*Academic Performance Rating Scale (APRS).* The APRS is a 22-item measure that asks teachers to rate different aspects of a child's academic performance in the classroom (DuPaul, Rapport, & Perriello, 1991). The APRS has three factors (DuPaul et al., 1991), two of which will be used in the present investigation: an Academic Productivity factor (7 items) that relates to work completion and accuracy, independent work, and following directions, and an Academic Success (12 items) factor related to the child's academic ability.

